### **5.1. SUBJECT DISPOSITION, DEMOGRAPHIC AND BASELINE CHARACTERISTICS**

Subject disposition will be presented for all subjects in the ITT population. The number of subjects who completed the study or early terminated from the study during the blinded treatment period will be provided. The reasons for early termination will be presented by treatment group. Additionally, the number of weeks on study will be summarized for all treated subjects.

Demographic data, including age, gender, race, ethnicity, and Fitzpatrick skin type, and screening weight (kg) and height(cm) will be summarized using descriptive statistics by treatment group. This information will be reviewed for baseline differences, but no statistical testing will be performed.

Baseline characteristics, including duration of alopecia, duration of current episode of patchy alopecia (continuous and dichotomized (< 2 years, >= 2 years), baseline hair pull test results (dislodged hairs and broken hairs), baseline SALT score group (<50%, >50%) and baseline Scalp-ClinRO and Scalp-PRO will be reported.

Alopecia treatment history will be summarized. The count and percent of subjects using the therapies pre-specified on the History of Alopecia CRF page will be reported.

Medical history will be summarized using the pre-specified CRF body system categories. The count and percent of subjects reporting a condition in the body system will be reported.

Findings from the baseline physical examination (PE) will also be summarized using the pre-specified body system categories and include reporting of abnormal not clinically significant and abnormal clinically significant.

Prior and concomitant medications will be coded using the World Health Organization (WHO) Drug Dictionary (version WHO-DD – March 2019) for the entire period of the study. Prior and concomitant medications will be summarized in tables and may be presented in data listings.

Study drug exposure and compliance will be summarized by treatment. The study drug duration along with summaries of missed doses, dose reductions, and treatment compliance will be reported.

## **5.2. EFFICACY ANALYSIS**

### **5.2.1. Primary Efficacy Endpoint**

The primary efficacy variable will be the mean percent change from baseline in the SALT score at Week 24 (Visit 10).

### **5.2.2. Primary Efficacy Analysis**

Descriptive statistics for the SALT score, change, and percent change from baseline will be presented for each scheduled analysis visit. Percent change from baseline in SALT over time up to Week 24 will be analyzed using a mixed effect for repeated measures (MMRM) model. This primary analysis will utilize the score with imputation for LOCF and will be based on the ITT population. The model will include fixed effect terms for treatment, study visit, baseline SALT score group (<50, >=50), and treatment by SALT group interaction. Within-subject variability will be modeled using a compound symmetry covariance structure. The least squares mean (LS Mean) percent change from baseline in the SALT score at each visit, estimated from the MMRM model, with the estimated standard error and 95% confidence interval (CI), will be presented in tabular and graphic format. The difference in the adjusted means between treatment groups and the associated 95% CI of the difference will be provided.

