11.4. Efficacy Analyses

11.4.1. Primary Efficacy Analyses

The primary efficacy variable will be the percent change from baseline in the SALT score at Week 24 (Visit 10). This represents the percentage of hair regrowth. It will be calculated as the mean of the changes from baseline (Visit 2) SALT score to Week 24 (Visit 10) SALT score, divided by the baseline SALT score and expressed as a percentage. Missing data for the primary endpoint will be imputed using Last Observation Carried Forward (LOCF) methodology. The analysis will be conducted on the relative percent change from baseline over time including all visits using a mixed effect model repeated measures (MMRM). The adjusted mean (LS Mean) for percent change from baseline in the SALT score at each visit, estimated from the MMRM, with the estimated standard error and 95% confidence interval (CI), will be presented in tabular and graphic

format. The difference in the adjusted means between treatment groups and the associated 95% CI of the difference will be provided. No adjustment for multiplicity will be made. The model will include fixed effect terms for treatment, study visit, baseline SALT score group (<50, ≥ 50), and treatment by SALT group interaction. The primary analysis will be based on the Intent-to-Treat (ITT) population. Statistical significance for primary efficacy endpoint will be declared if at least one treatment group comparison at the Week 24 visit has a two-sided p-value less than or equal to 0.05.

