### **3. GENERAL STATISTICAL CONSIDERATIONS**

#### **3.1. SAMPLE SIZE AND POWER**

The planned sample size is 120 subjects. Since this is the first multicenter study evaluating the effect of ATI-50002 Topical Solution in subjects with stable patchy alopecia areata, the sample size was based upon feasibility issues rather than on a formal power calculation. However, data from 120 subjects (40 per group), utilizing LOCF for missing data, provides 80% power to detect a 24-point difference in percent change from baseline in SALT score between any two treatment groups. This power computation was based upon the assumed standard deviation of 38%. Data from a previous study NCT02197455 showed that the standard deviation in percent change from baseline in the SALT score is 30.3%. The 38% standard deviation assumption used for this power computation was chosen to account for the increase in variance due to the lower baseline SALT entry criteria for this study as compared to NCT02197455.

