#### **3.3.4. Missing Data and Outliers**

For missing clinical assessments, the method of last observation carried forward (LOCF) will be used to impute values. The last non-missing value prior to the missing assessment will replace the missing values. For subjects who terminate early, missing assessment after the date of early termination will be replaced by the LOCF method.

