## **5. STATISTICAL METHODS**

Descriptive statistical methods will also be used to summarize the data from this study, with hypothesis testing performed for the primary and key secondary efficacy endpoints. Unless stated otherwise, the term “descriptive statistics” refers to number of subjects, mean, median, standard deviation, minimum, and maximum for continuous data, and frequencies and percentages for categorical data. For categorical variables, the denominator of percentages will be the number of subjects in the treatment group, except for those collected by study visit and/or scheduled time point, in which case the denominator of percentages will be the number of subjects with a non-missing value at the visit and/or the scheduled time point. If a different denominator is used, this will be identified in the summary table.

All data collected during the study will be included in data listings. Unless otherwise noted, the data will be sorted first by treatment group, subject number, and then by date within each subject number. Assessments indicated as ‘Not Done’ will not be included in the listings.

The term ‘treatment group’ refers to ATI-50002 active groups and matching Vehicle group.

All statistical testing will be two-sided and will be performed using a significance (alpha) level of 0.05 unless otherwise stated. P-values will be presented to three decimal places. For the efficacy endpoints, the ATI-50002 treatment groups will be tested versus vehicle via statistical inference.

The statistical analyses will be conducted with the SAS® software package version 9.4 or higher. All analyses will be subject to formal verification procedures. Specifically, results will be independently verified by a second programmer/statistician or independently hand-checked prior to issuance of the draft statistical report. All documents will be reviewed by the lead statistician to ensure accuracy and consistency.

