### **5.2.3. Additional Analyses of the Primary Endpoint**

The statistical methods for the main analysis will be repeated using the PP population. The analysis will also be performed using the observed data without imputation for missing in both the ITT population and the PP population.

Another exploratory MMRM analysis for the primary endpoint will be performed with factors for the duration of current episode of patchy alopecia (< 2 years, >= 2 years) and the treatment by duration of episode interaction replacing the baseline SALT score group and treatment by SALT group interaction factors. This analysis will be performed in both the ITT population and the PP population using data with LOCF imputation.

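### LOCF filling before the primary MMRM is unnecessary and can bias the Week 24 SALT difference if subjects leave early; the cure needs observed data and a treatment-by-visit model

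*SAP*

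**What the plan says.** SAP 5.2.2 (Primary Efficacy Analysis) analyses percent change in SALT up to Week 24 by MMRM and states: "This primary analysis will utilize the score with imputation for LOCF and will be based on the ITT population". The fixed effects are treatment, visit, baseline SALT group (split at 50) and treatment-by-SALT-group. Within-subject covariance is compound symmetry. There is no treatment-by-visit term.

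Protocol 11.4.1 matches: "Missing data for the primary endpoint will be imputed using Last Observation Carried Forward (LOCF) methodology". It ties the declaration of significance to the Week 24 comparison.

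SAP 3.3.4 sets the general rule for missing clinical assessments: "the method of last observation carried forward (LOCF) will be used to impute values". Each gap takes the single most recent earlier value, and nothing is added for imputation uncertainty.

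SAP 5.2.3 plans the analysis without filling as an additional analysis: "The analysis will also be performed using the observed data without imputation for missing in both the ITT population and the PP population". The ITT version is proposed Table 14.2.1.4; the LOCF primary is Table 14.2.1.2.

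The power statement in SAP 3.1 and Protocol 11.1 rests on "data from 120 subjects (40 per group), utilizing LOCF for missing data". Neither document gives an expected dropout rate, a missing-data assumption or a reason for LOCF.

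**The concern.** An MMRM already uses the visits a subject completed before leaving. Adding LOCF contributes no data, only the claim that the score would not have moved again. The protocol gives reasons to doubt that. Its amendment history extends treatment from 3 to 6 months, and its disease overview (2.1) describes patchy disease as waxing and waning with common spontaneous regrowth. An early value is then a poor stand-in for Week 24 in either arm.

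The discontinuation visit does not remove the problem. Protocol 5.9 asks for Visit 10 assessments when a subject stops early, but SAP 3.3.7 assigns double-blind assessments to windows by study day, and Week 24 covers Days 155 to 182. An exit visit on Day 60 falls in the Week 8 window (Days 43 to 70) and is carried forward from there. The per-protocol analysis cannot expose the effect of early leaving either, since SAP 4.3 excludes anyone who did not complete Week 24.

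At stake are the size of the primary Week 24 difference and, with unequal dropout, some false difference under no effect.

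**Working it through.** **Inputs from the documents.** 40 per group, a 24-point difference and SD 38 (SAP 3.1); two-sided alpha 0.05 (SAP 5); efficacy visits at Weeks 4, 8, 12, 16, 20 and 24.

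**Assumptions (not in the documents).** Regrowth is counted as positive and is linear to Week 24. The last observed visit of a leaver is uniform over Weeks 0, 4, 8, 12, 16 and 20, so its mean is Week 10. Dropout is 10 to 30% per arm, and up to 40% in one extreme case.

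**1. The plan's own power figure.** SE = 38 × √(2/40) = 8.50. 24/8.50 = 2.82, and 2.82 − 1.96 = 0.86, giving 80.6% power (79.7% with the noncentral t). The stated 80% reproduces.

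**2. Raw Week 24 LOCF difference.** A leaver loses on average 1 − 10/24 = 7/12 of the Week 24 change. Let V be vehicle regrowth, E the drug effect, and dA and dV the dropout proportions in the active and vehicle arms. The expected difference is E − (7/12) × [dA(V + E) − dV·V].
- Equal dropout d, E = 24: 24 × (1 − 7d/12) = **22.6, 21.2, 19.8** at 10, 20, 30%. A simulation of 20,000 runs gave 22.6, 21.1, 19.8.
- Active 30%, vehicle 10%, V = 8: 24 − (7/12) × (9.6 − 0.8) = **18.9**. Simulation gave 18.9.
- d = 0 in both arms: 24, no bias.
- No drug effect, V = 20, active 10% and vehicle 30 to 40%: (7/12) × 20 × (0.2 to 0.3) = **2.3 to 3.5** points of false difference. Simulated type I error was 5.8 to 7.4%.

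**3. Dropout driven by poor response** (400 runs per scenario, V = 8, Monte Carlo error about 0.4 points). The raw LOCF difference was 23.5/22.8/21.6 at nominal 10/20/30% in both arms. It was 23.8 with vehicle 30% and active 10%, and 21.1 with the rates reversed. Observed data with treatment-by-visit and unstructured covariance gave 23.3 to 24.4 in all scenarios with E = 24, random or response-driven.

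**4. The SAP's own model.** With no treatment-by-visit term, compound symmetry and complete data, the treatment difference is the average over visits: 24 × (4 + 8 + 12 + 16 + 20 + 24)/(6 × 24) = **14.0** (simulated 13.9). Under LOCF, leavers last seen at Weeks 0, 4, 8, 12, 16, 20 have visit averages 0, 4, 7.33, 10, 12, 13.33, mean 7.78. The expected estimate is 14 − 6.22d/1:

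| Dropout, both arms | LOCF, arithmetic | LOCF, simulated | Observed data, simulated |
|---|---|---|---|
| 10% | 13.4 | 13.2 | 13.3 |
| 20% | 12.8 | 12.8 | 13.2 |
| 30% | 12.1 | 11.8 | 12.3 |

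The simulations omit the SALT-group terms. LOCF costs 0.1 to 0.5 points against observed data here. Under no effect, the false difference of step 2 shrinks to (20/24) × 6.22 × (0.2 to 0.3) = 1.0 to 1.6 points. Simulated type I error was 5.8% and, with 40% vehicle dropout, 8.8% (Monte Carlo error about 1.1 to 1.4 points).

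**5. Standard errors** (same simulation as step 3). The LOCF standard error at Week 24 averaged 7.8 to 8.5, against an empirical SD of 7.5 to 8.6. With V = 8 and no effect, the mean error was at most about 1 point and type I error was 4 to 7%.

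**6. Power with an explicit dropout rate.** On completers alone (36, 32, 28 per group), SE = 8.96, 9.50, 10.16 and power = 76%, 71%, 66%. The 20,000-run LOCF Week 24 test had 77%, 73%, 70%, so LOCF does not keep the 80% either.

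**The case against.** The strongest objection is that the raw Week 24 figures do not come from the SAP's model. That stands. In that model the extra loss from LOCF is a fraction of a point, and the missing treatment-by-visit term matters far more. It follows that promoting Table 14.2.1.4 as planned would not recover the Week 24 effect. With 30% vehicle and 10% active dropout for poor response, the planned model gave 12.4 on observed data and 14.2 on LOCF data, so the change of data set alone moved further from 24.

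It is also fair that SAP 5.2.3 already makes a divergence visible, that this Phase 2 study was sized on feasibility, and that Protocol 5.9 seeks an exit assessment, so fewer leavers may lack any post-baseline value than assumed. Inclusion criterion 3 requires no current spontaneous regrowth, so a 20-point vehicle change is a demanding case. These points limit the size of the problem; none of them is a reason to impute.

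A reader might infer more than the documents support:
- That the Week 24 effect is certainly biased. There is no bias without missing data, and no dropout rate is given.
- That copied values count as independent information. The model correlates visits within subject, and the standard errors in step 5 were close to correct.
- That LOCF makes an early leaver a Week 24 responder. SAP 3.3.4 could be read that way, but SAP 5 uses non-missing denominators for by-visit percentages, SAP 5.2.5 speaks of observed proportions, and the responder tables carry no LOCF label. The rule is unclear rather than shown to be wrong.
- That both analyses are already programmed. SAP 8.1 lists proposed tables only.

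**Conclusion.** The point holds in a conditional form. LOCF before a likelihood MMRM is unnecessary and unjustified in either document. It can bias the Week 24 difference when subjects leave while scores are still changing, even if they leave completely at random.

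Under linear onset, uniform timing of dropout and equal dropout of 10 to 30%, the raw Week 24 difference falls by 1.4 to 4.2 points from 24. Unequal dropout with a vehicle arm moving 20 points can create a false difference of about 2 to 3.5 points, with type I error of about 6 to 7% for the raw comparison in extreme cases. Attenuation and lost power are the firmer argument; type I inflation is small in most scenarios.

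The SAP's model estimates a visit average, so the data set and the model must change together. All sizes rest on the assumed course and dropout.

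**What to change.** - In SAP 5.2.2, Protocol 11.4.1 and the protocol synopsis, make the ITT MMRM on observed data primary. Add treatment-by-visit, use an unstructured covariance with a stated fallback if it does not converge, and define the primary contrast as the Week 24 difference of each active arm from vehicle.
- Move the LOCF version (Table 14.2.1.2) to sensitivity and narrow SAP 3.3.4 accordingly. State the missing-at-random assumption.
- Restate power in SAP 3.1 and Protocol 11.1 with an expected dropout rate. The completers-only 76/71/66% at 10/20/30% is a conservative guide, because the MMRM also uses leavers' earlier visits.
- Confirm that the ALODEX, SALT change and DLQI analyses, which borrow the primary method (SAP 5.2.5), follow the change. Separately, state one missing-data rule for the responder endpoints.

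The cost is wording in both documents and a modest model change; both tables are already on the proposed list. The downside is a slightly wider confidence interval and a lower stated power. The change should be made before the unblinding described in SAP 3.4.1.

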The planned sample size is 120 subjects. Since this is the first multicenter study evaluating the effect of ATI-50002 Topical Solution in subjects with stable patchy alopecia areata, the sample size was based upon feasibility issue rather than on a formal power calculation. However, data from 120 subjects (40 per group), utilizing LOCF for missing data, provides 80% power to detect a 24-point difference in percent change from baseline in SALT score between any two treatment groups. This power computation was based upon the assumed standard deviation of 38%. Data from a previous study NCT02197455 showed that the standard deviation in percent change from baseline in the SALT score is 30.3%. The 38% standard deviation assumption used for this power computation was chosen to account for the increase in variance due to the lower baseline SALT entry criteria for this study as compared to NCT02197455.

Statistical Methods

The primary efficacy variable will be the percent change from baseline in the SALT score at Week 24 (Visit 10). This represents the percentage of hair regrowth. It will be calculated as the mean of the changes from baseline (Visit 2) SALT score to Week 24 (Visit 10) SALT score, divided by the baseline SALT score and expressed as a percentage. Missing data for the primary endpoint will be imputed using Last Observation Carried Forward (LOCF) methodology. The analysis will be conducted on the relative percent change from baseline over time including all visits using a mixed effect model repeated measures (MMRM). The adjusted mean (LS Mean) for percent change from baseline in the SALT score at each visit, estimated from the MMRM, with the estimated standard error and 95% confidence interval (CI), will be presented in tabular and graphic format. The difference in the adjusted means between treatment groups and the associated 95% CI of the difference will be provided. No adjustment for multiplicity will be made. The model will include fixed effect terms for treatment, study visit, baseline SALT score group (<50 , ≥ 50), and treatment by SALT group interaction. The primary analysis will be based on the Intent-to-Treat (ITT) population. Statistical significance for primary efficacy endpoint will be declared if at least one treatment group comparison at the Week 24 visit has a two-sided p-value less than or equal to 0.05.

Secondary Efficacy Analyses

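### The primary MMRM lists no treatment-by-visit term, so it estimates a Week 4 to 24 average difference, not the Week 24 comparison that the endpoint and success rule require

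*SAP*

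**What the plan says.** SAP 5.2.1 and the protocol's endpoint list place the primary variable, percent change from baseline in SALT, at Week 24. Protocol 11.4.1 and the synopsis declare success "if at least one treatment group comparison at the Week 24 visit has a two-sided p-value less than or equal to 0.05".

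For the analysis, SAP 5.2.2 states: "Percent change from baseline in SALT over time up to Week 24 will be analyzed", using an MMRM on LOCF-imputed ITT data. The fixed effects are given as "The model will include fixed effect terms for treatment, study visit, baseline SALT score group (<50, >=50), and treatment by SALT group interaction". Protocol 11.4.1 agrees ("The model will include fixed effect terms for treatment, study visit, baseline SALT score group (<50, ≥ 50), and treatment by SALT group interaction"), and so does the synopsis. On covariance the SAP says: "Within-subject variability will be modeled using a compound symmetry covariance structure". Both documents promise LS means by visit, and SAP 5.2.8 plots them over time by arm.

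No other section supplies a treatment-by-visit term:

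- SAP 5.2.3 carries the model over unchanged ("The statistical methods for the main analysis will be repeated using the PP population"), also to observed data. Its exploratory model only swaps the SALT-group terms for episode-duration terms.
- SAP 5.2.5 reuses the method for percent change in ALODEX, change in SALT, change in ALODEX, and DLQI.
- SAP 5.2.7 repeats the primary analysis in the whole-scalp subset. In the SALT subgroups it only drops the SALT-group factor.
- SAP 6 records no departure from the protocol.

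**The concern.** A model with visit only as a main effect lets the overall level move over time but keeps the gap between arms fixed. Treatment by SALT group does not help, because it varies the effect by baseline stratum and not by time. The LS-mean curves would be parallel, and the difference printed for Week 24 would be the one printed for Week 4.

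That matters because this one test decides whether the trial is declared positive. Where regrowth builds up over the six months, the reported difference understates the Week 24 effect and its confidence interval misses it too often. Where an early effect fades, the same output can declare a Week 24 effect that is absent. The 80% power statement also describes a different test from the one specified.

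**Working it through.** **Inputs.** From SAP 3.1: 40 per arm, SD 38, a 24-point difference, 80% power. From SAP 5: two-sided 0.05. From SAP 5.2.2: the fixed effects, compound symmetry and LOCF. From the schedule of assessments: SALT after baseline at Weeks 4, 8, 12, 16, 20 and 24. The time courses, the correlations and the SD at earlier visits are my assumptions.

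**1. The plan's power figure.** SE = 38 × √(2/40) = 8.50 and 24/8.50 = 2.82. A noncentral t with 114 df gives 80.0% (normal approximation 80.6%). The stated 80% therefore reproduces, as the power of a single-visit contrast.

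**2. What the listed model estimates.** The mean for arm a, SALT group g, visit v is μ + τ(a) + ν(v) + γ(g) + τγ(a,g). The difference from vehicle is [τ(a) − τ(0)] + [τγ(a,g) − τγ(0,g)], which does not contain v. With all six visits filled and compound symmetry, each visit has weight w = 1/6, so the estimate is the plain average of the six by-visit differences.

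- One simulated three-arm trial (unequal SALT groups, about 20% dropout filled by LOCF): the listed terms gave −13.634 and −10.811, equal to the averages of the adjusted by-visit differences. With treatment-by-visit added, the Week 24 contrasts were −18.55 and −18.06.
- 100 simulated trials with a true difference running from −4 to −24: the listed model averaged −13.92 at every visit. With the interaction the means were −3.9, −8.1, −12.0, −15.8, −20.1 and −23.7.

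**3. Target, coverage and power.** SE of the average = √(w′Sw × 2/40), where S is the covariance matrix over visits. For compound symmetry and SD 38 this is 8.50 × √((1 + 5ρ)/6), so ρ = 0.5 gives 6.49. For a linear rise the target is (4 + 8 + 12 + 16 + 20 + 24)/6 = 14. Then 14/6.49 = 2.16, giving 57% power, and the bias is (24 − 14)/6.49 = 1.54 SE, giving 67% coverage of the Week 24 value.

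The ranges below cover compound symmetry 0.5–0.8 and AR(1) 0.7–0.95. Each cell shows SD 38 at every visit / SD rising linearly from 19 to 38.

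| True difference at Weeks 4, 8, 12, 16, 20, 24 | Target | 95% CI coverage of Week 24 value | Power as written |
|---|---|---|---|
| Constant: 24 throughout | 24 | 95% / 95% | 84–96% / 97% or more |
| Plateau: 8, 16, 24, 24, 24, 24 | 20 | 90–92% / 87–90% | 69–87% / 90–98% |
| Linear: 4, 8, 12, 16, 20, 24 | 14 | 66–77% / 46–63% | 40–59% / 63–82% |
| Late: 0, 0, 6, 12, 18, 24 | 10 | 41–60% / 18–37% | 23–34% / 37–54% |

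**4. The opposite error.** For 24, 20, 15, 10, 5, 0 the target is 74/6 = 12.3. With SD 38, the test reported for Week 24 rejects in about 32–48% of trials (correlations as above, with compound symmetry up to 0.9), although the true Week 24 difference is zero.

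**5. DLQI.** It is collected after baseline only at Weeks 4, 12 and 24. The model targets (8 + 24 + 24)/72 = 78% of the Week 24 effect under plateau, (4 + 12 + 24)/72 = 56% under linear rise, and (0 + 6 + 24)/72 = 42% under late onset.

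**6. Covariance once the term is added.** If the SD rises from 19 to 38, compound symmetry pools it to √(mean of the six variances) = 29.2. The Week 24 SE is then 29.2/38 = 0.77 of the true one, and coverage is P(|Z| < 1.96 × 0.77) = 87%. The reverse change, unstructured covariance without the interaction, weights visits by S⁻¹1/(1′S⁻¹1). Under rising SD the linear-rise target would then lie between −4.5 and 7.7, depending on the correlation.

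**The case against.** The strongest reply is that the interaction was intended and merely left off the list. The text does not say that only these terms enter, and the by-visit LS means, the plots and the Week 24 success rule all presuppose it. That may well be so. But the list names one interaction explicitly, and SAP 5.2.3 and 5.2.7 edit it term by term as if it were complete. Two programmers following it could produce different primary p-values.

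It is also true that software would still print a Week 24 difference and p-value from the additive model. They are Week 24 results only if the effect is constant, which neither document assumes. Strictly, there is one difference per SALT group, and the overall contrast depends on a group weighting that the documents do not state.

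Three further points stand:

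- The by-visit descriptive SALT tables would expose a divergence, and the logistic and Wilcoxon analyses are unaffected. Neither replaces the primary test.
- The sample size rests on feasibility, so lost power is the lesser argument. Estimating the wrong quantity is the main one.
- The 80% after the fix assumes an even SALT-group split. With equally weighted groups and SD 38 within each, power is 78% at 60/40, 73% at 70/30 and 61% at 80/20. Adjustment could also lower the residual SD.

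The covariance advice rests on an assumed rise in SD and is a companion to the fix, not part of the defect.

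**Conclusion.** The primary model is wrong as written for a Week 24 endpoint and must be corrected. The omission itself is certain from the text and is the same in both documents. Its size is not known. A true 24-point Week 24 effect becomes a target of 24, 20, 14 or 10 points across the four profiles, and power as written runs from 23% to over 97%, depending on profile, correlation and SD.

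The test of no effect at any visit remains valid, but a test of no effect at Week 24 does not. If the effect is constant from Week 4, the listed model is unbiased and more precise. With an early plateau and rising SD it has more power, though for a different quantity. The problem carries into every analysis that reuses the model.

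**What to change.** In SAP 5.2.2, protocol 11.4.1 and the synopsis:

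1. Add treatment-by-visit to the fixed effects.
2. State that the primary test is the active-minus-vehicle LS-mean contrast at Week 24 from that model.
3. Carry both changes through to the PP, observed-data, ALODEX, SALT-change, DLQI, exploratory-duration and subset MMRMs.
4. Use a covariance that lets the variance differ by visit, such as unstructured. Do not make this change without the interaction.

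Settle this before the unblinding described in SAP 3.4.1, because choosing the term afterwards would be data-driven. Stating how the SALT groups are weighted in the LS means would close the remaining ambiguity.

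The cost is wording, one model term and one named contrast, with no new data or patients. If the effect is in fact constant, precision is lost: the Week 24 SE is 1.05–1.33 times that of the average at SD 38, or 1.4–1.8 times under rising SD. Power is then 80% in place of 84–96%, or of 97% or more. With an early plateau and rising SD it is 80% in place of 90–98%. These 80% figures assume an even SALT-group split.
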